### 5. STATISTICAL ANALYSIS

## 5.1. GENERAL METHODOLOGY

Experimental results will be summarized using descriptive statistics according to data type (n, mean, standard deviation or standard error, median, and range for continuous endpoints; number and percent of subjects in each category for categorical endpoints).

The estimated median time to event and its 95% confidence interval (CI) will be calculated (if at least 50% of subjects in the Full Analysis Set achieved the event) using the Kaplan-Meier estimator. The Kaplan-Meier estimates will also be displayed graphically.

All analyses will be presented by C1 Inhibitor 1000U only. Study drug administrations were planned according to subjects age; 500U for Subjects 2 to 5 years of age and 1000U for Subjects 6 years of age and older. However, only the higher dose of 1000U were administered.

Unscheduled visits data will not be included in analysis, otherwise specified. Unscheduled visits data will merely be presented in listings.

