## 5.2. ANALYSIS POPULATIONS

Enrolled subjects are all subjects who signed signed informed consent and completed screening.

All treated subjects (ie, Intent-to-Treat Safety [ITT-S] Population: subjects who receive any amount of study drug) will be included in the safety analyses.

Full Analysis Set Population (defined as subjects who have at least one post baseline efficacy assessment) will be included in the efficacy analyses.

All subjects with evaluable PK/PD profiles (ie, PK/PD Population) will be included in PK/PD analyses as appropriate.

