#### 5.7.2. TREATMENT OF BREAKTHROUGH ANGIOEDEMA ATTACKS

A breakthrough attack is defined as an angioedema attack that occurs during long-term prevention therapy with CINRYZE® (i.e, between first study drug and last study drug dose).

The following efficacy endpoints for treatment of breakthrough angioedema attacks will be assessed by CINRYZE® treated attacks, non-CINRYZE® C1-INH treated attacks and all other attacks (including any medications other than C1-INH and untreated attacks):

- The number of subjects with breakthrough angioedema attacks.
- The number of subjects with 1, 2, 3 or more angioedema attacks.
- The number of subjects who achieve initial improvement and Complete Resolution.
- Time to initial improvement and time to Complete Resolution.

Additional analysis for breakthrough angioedema attacks treated with CINRYZE® will also be presented for:

- The number of subjects with breakthrough angioedema attacks.
- The number of subjects with 1, 2, 3 or more angioedema attacks.
- Time from onset of attack to time treated by CINRYZE.
- The number of subjects who achieve initial improvement and Complete Resolution. Complete Resolution is defined as the cessation of all symptoms of the breakthrough angioedema attack since onset of attack.
- Time from the start of study drug administration, CINRYZE°, for the particular attack to the time of initial improvement and time to Complete Resolution.

\\SW20RND01\\VistaTempDir\Temp28232\Shire\_0624\_209\_SAP\_v1 0.docx Document: Version Number:

Version Date: 21Jul2017

Template No: CS\_TP\_BS016 Revision 4

Effective Date: 01Apr2016

Author:

Copyright © 2009, 2010, 2012, 2016 Quintiles Transnational Corp. All rights reserved.

The contents of this document are confidential and proprietary to Quintiles Transnational Corp. Unauthorized use, disclosure or reproduction is strictly prohibited.

Shire
PROTOCOL: 0624-209
Page 18 of 35

Derivations will be constructed as follow:

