#### **Time to Complete Resolution**

Time to complete resolution is defined as the time from the onset of attack to complete resolution of symptoms.

The analysis of the time to event endpoint includes only the first attack from each subject meeting the treatment criterion since attacks experienced by the same subject are dependent. Median time to complete resolution and the corresponding 95% CI estimated using the Kaplan-Meier method will be summarized.

Kaplan Meier plots for time from CINRYZE® to initial improvement and to complete resolution will also be presented.

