## 9. APPENDICES

# 9.1. APPENDIX I – LIST OF STATISTICAL OUTPUTS

#### 9.1.1. LIST OF PLANNED TABLES

Table 14.1.1.1 Subject Disposition (All Screened Subjects)

Table 14.1.2.1 Protocol Deviations (Intent-to-Treat Safety Analysis Set)

Table 14.1.4.1 Demographic and Baseline Characteristics (Intent-to-Treat Safety Analysis Set)

Table 14.1.4.3.1 Summary of HAE History (Intent-to-Treat Safety Analysis Set)

Table 14.1.4.3.2 Summary of Medical History (Intent-to-Treat Safety Analysis Set)

Table 14.1.4.4 Prior Medications and Therapy (Intent-to-Treat Safety Analysis Set)

Table 14.1.4.5 Concomitant Medications and Therapy (Intent-to-Treat Safety Analysis Set)

Table 14.2.1.1 Summary of Angioedema Attacks during Treatment Period (Full Analysis Set)

Table 14.2.1.2.1 Sensitivity Analysis Completed Schedules - Summary of Angioedema Attacks during Treatment Period (Full Analysis Set)

Table 14.2.1.2.2 Sensitivity Analysis Treatment Compliance - Summary of Angioedema Attacks during Treatment Period (Full Analysis Set)

Table 14.2.1.3 Analysis of Clinical Responder Rate – Achieving at least 50%, 70% or 90% Reduction Relative to Historical Data in NNA (Full Analysis Set)

Table 14.2.2.1.1 Summary of Breakthrough Angioedema Attacks Treated By CINRYZE (Full Analysis Set)

Table 14.2.2.1.2 Summary of Breakthrough Angioedema Attacks Treated By Non-CINRYZE C1-INH (Full Analysis Set)

Table 14.2.2.1.3 Summary of Other Breakthrough Angioedema Attacks Not Treated with C1-INH (Full Analysis Set)

Table 14.2.2.1.4 Summary and Change from Baseline on AE-QoL (Full Analysis Set)

Table 14.2.3.1 C1-INH Antigen, Functional C1-INH activity, Complement C4 and C1q (Intent-to-Treat Safety Analysis Set)

Table 14.2.3.2 Antibody Results (Intent-to-Treat Safety Analysis Set)

Table 14.3.1.1 Overall Treatment-emergent Adverse Events (TEAEs) (Intent-to-Treat Safety Analysis Set)

Table 14.3.1.2.1 Treatment-emergent Adverse Events by System Organ Class and Preferred Term (Intent-to-Treat Safety Analysis Set)

Document: \\SW20RND01\\VistaTempDir\Temp28232\\Shire\_0624\_209\_SAP\_v1 0.docx

Version Date: 21Jul2017

Version Number:

1.0

Template No: CS TP BS016 Revision 4 Reference: CS WI BS005

Effective Date: 01Apr2016

Author:

Table 14.3.1.2.2 Serious Treatment-emergent Adverse Events by System Organ Class and Preferred Term (Intent-to-Treat Safety Analysis Set)

Table 14.3.1.3.1 Treatment-emergent Adverse Events by Preferred Term (Intent-to-Treat Safety Analysis Set)

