#### 9.1.2. LIST OF PLANNED FIGURES

Figure 14.2.2.1.1.1 Kaplan Meier Plot - Time from Cinryze to Initial Improvement (Full Analysis Set)

Figure 14.2.2.1.1.2 Kaplan Meier Plot - Time from Cinryze to Complete Resolution (Full Analysis Set)

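### SAP 5.1 ties the Kaplan-Meier median for breakthrough-attack times to half of the whole Full Analysis Set, while SAP 5.7.2 analyses only subjects with a qualifying attack

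*SAP*

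**What the plan says.** - **Condition (SAP 5.1, General Methodology).** The KM median time to event and its 95% CI are to be calculated "if at least 50% of subjects in the Full Analysis Set achieved the event".
- **Denominator (SAP 5.2, Analysis Populations).** The FAS is "defined as subjects who have at least one post baseline efficacy assessment". No attack is needed to belong to it.
- **Who is on the curve (SAP 5.7.2, Time to Complete Resolution).** "The analysis of the time to event endpoint includes only the first attack from each subject meeting the treatment criterion". The clock starts with the attack: "Time to complete resolution is defined as the time from the onset of attack to complete resolution of symptoms". The additional CINRYZE analysis starts it at the CINRYZE dose given for that attack.
- **Split.** SAP 5.7.2 divides attacks into three categories: treated with CINRYZE, treated with another C1 inhibitor, and all others.
- **Endpoint-specific statement (same section).** "Median time to complete resolution and the corresponding 95% CI estimated using the Kaplan-Meier method will be summarized". The 50% condition is not repeated here. No matching statement is made for initial improvement.
- **Output labels (SAP 9.1).** Outputs that can only contain subjects with a qualifying attack still carry the FAS label, for example "Kaplan Meier Plot - Time from Cinryze to Complete Resolution (Full Analysis Set" and "Summary of Breakthrough Angioedema Attacks Treated By Non-CINRYZE C1-INH (Full Analysis Set".

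**The concern.** The reporting condition and the estimator use different populations. A subject with no attack in a category has no starting time and cannot have the event, yet counts against the 50%. Such subjects cannot be treated as censored observations, because 5.7.2 keeps them out of the analysis.

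The condition also works against the prevention aim: the fewer subjects have attacks, the harder it is to meet, however quickly the attacks that do occur resolve.

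Treatment of breakthrough attacks is part of a stated objective (Protocol 2). SAP 6.2 drops the clinical-relief analysis for want of data, so the counts and times for improvement and resolution carry that objective. What is at stake is whether a median and CI appear in the table, and whether two programmers reading 5.1 and 5.7.2 would produce the same table. The analyses are descriptive, so no error rate is involved.

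**Working it through.** The 50% threshold is a rule, so there is no figure in the plan to reproduce. The check applies the rule as written.

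**Inputs from the documents.** At least 6 completers (SAP 3.2); overseas 12-week attack rates of 6.3 on CINRYZE and 12.8 on placebo (Protocol 1.1.2); an entry minimum of one attack per month (Protocol 4.1); 30.4 days per month (SAP 5.7.1).

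**Assumed, because not given.** The FAS size N, and the share p of attacks that falls in a category.

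**1. Events needed** = N/2, rounded up.

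| FAS (N) | Events needed | A reached median is withheld with |
|---|---|---|
| 6 | 3 | 1 to 2 events |
| 8 | 4 | 1 to 3 events |
| 10 | 5 | 1 to 4 events |

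**2. Examples.**
- N = 6, two contributors, both resolve: the curve falls to 0, but 2/6 = 33%, so the median is withheld.
- N = 6, four contributors, two resolve and the other two are censored later: S = (3/4) × (2/3) = 0.50, so the median is reached, but 2/6 = 33% fails.
- N = 8, three contributors, all resolve: 3/8 = 38% fails.

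The loss is therefore not confined to one or two contributors.

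**3. The error runs one way.** Let n ≤ N subjects contribute and d have the event. At the i-th event the risk set is at most n − i + 1, so the final KM value is at most (n − d)/n = 1 − d/n. If d ≥ N/2, then d/n ≥ 1/2 and S ≤ 0.5. Meeting the condition guarantees a reached median, but a reached median does not guarantee that the condition is met. In a simulation of 50,000 data sets (N from 6 to 10, random censoring), 11,782 met the condition and the median was reached in every one. Of 33,706 with a reached median, 21,924 failed the condition. That second proportion depends on the simulated mix and shows direction only.

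**4. How often (illustrative).** Take N = 6, Poisson attack counts and every qualifying attack resolving. With q = 1 − exp(−λp), the chance of withholding a reached median is

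P(1 ≤ X ≤ 2) = 6q(1 − q)^5 + 15q²(1 − q)^4.

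Two anchors for λ, the attacks per 12 weeks: the overseas on-CINRYZE rate of 6.3, and a low value of (84/30.4) × (6.3/12.8) = 1.36, which puts every subject at the entry minimum and applies the overseas ratio.

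| λ | p | q | P(withheld) |
|---|---|---|---|
| 6.3 | 0.05 | 0.270 | 0.646 |
| 6.3 | 0.10 | 0.467 | 0.384 |
| 6.3 | 0.20 | 0.716 | 0.058 |
| 6.3 | 0.50 | 0.957 | <0.001 |
| 1.36 | 0.10 | 0.127 | 0.527 |
| 1.36 | 0.25 | 0.288 | 0.636 |
| 1.36 | 0.50 | 0.493 | 0.339 |
| 1.36 | 0.75 | 0.639 | 0.127 |
| 1.36 | 1.00 | 0.743 | 0.041 |

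Variation between subjects lowers q. With a negative binomial, k = 1, q = 1 − 1/(1 + λp): λ = 1.36, p = 0.50 gives q = 0.405 and P = 0.490; λ = 6.3, p = 0.10 gives q = 0.387 and P = 0.519.

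**5. Precision of what would be released.** With two contributors who both resolve, S = 0.50 after the first event. The log-log 95% interval is 0.50^7.38 to 0.50^(1/7.38), that is 0.006 to 0.910, where 7.38 = exp(1.96 × √0.5/ln 2). S is 0 after the second event, so the median has no estimable upper limit. The log-log method is an assumption; the SAP names none.

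**The case against.** **The specific rule may prevail.** SAP 5.7.2 promises the Complete Resolution median without any condition, and an endpoint-specific statement usually overrides a general one. This stands in part: for that endpoint withholding is possible, not certain. It does not help initial improvement, for which 5.1 is the only rule.

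**The phrase may be loose drafting.** The FAS label sits on every efficacy output, including those that only subjects with attacks can enter. The parenthesis may simply mean that the median is given if it is reached. That is plausible, but the words say otherwise, and a programmer would be entitled to follow them.

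**Suppressing tiny-sample medians is reasonable.** A median from one or two people says little. This is fair as a matter of presentation, but the SAP gives no such rationale and the condition serves it poorly: its cut-off moves with FAS size, not with the number contributing, and it can also block three of three resolved attacks at an FAS of 8.

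**Little is lost.** This largely stands. The category counts ("The number of subjects who achieve initial improvement and Complete Resolution"), the listings and the two CINRYZE KM plots carry no such condition. SAP 5.7.1 also gives an average attack duration, though not split by treatment. The ordinary descriptive statistics of 5.1 may supply a simple median when every attack resolves.

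**A stronger reading.** A reader might infer that the breakthrough-attack result for CINRYZE will be lost. The documents do not support that. Large probabilities arise only for lightly used categories, and at the overseas rate a category taking half of the attacks is almost never affected.

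**Conclusion.** The point holds as a minor one. As written, SAP 5.1 uses the wrong denominator for the 5.7.2 time-to-event summaries. The condition adds nothing to the check on whether the curve reaches 50%, and it can withhold a median that has been reached. That follows from the text and from steps 1 to 3, with no assumption about attack rates. For Complete Resolution the conclusion is narrower: 5.1 and 5.7.2 conflict or are ambiguous, and must be reconciled.

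The frequency is not known. The figures in step 4 rest on an FAS of 6 (the completer minimum, not a stated FAS size), assumed category shares, borrowed overseas rates and every attack resolving. They show a negligible effect for a category that takes most attacks and a possibly material one for a rarely used category. They are not forecasts for this trial.

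**What to change.** Replace the parenthesis in SAP 5.1 with a rule to this effect: the median and 95% CI are reported whenever the KM curve among subjects contributing a first attack in that treatment category reaches 50%; otherwise the median is shown as not reached; the number of contributing subjects and events is always shown; and CI limits that cannot be estimated are marked so. Put the same sentence in 5.7.2 for both initial improvement and Complete Resolution, so that the two sections agree. Record it as a dated change to the SAP.

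The cost is one sentence and minor programming, with no new data. The downside is that some reported medians will rest on very few subjects and be very imprecise, which is why the counts must stand beside them.

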#### 5.8.2. **CLINICAL LABORATORY EVALUATION**

Laboratory values will be obtained for hematology, clinical chemistry, coagulation, virology and urinalysis at the time points specified in Schedule 1 and Schedule 3 of the protocol. The laboratory tests will be performed by a central laboratory.

Descriptive statistics will be provided hematology, clinical chemistry and coagulation data at time points specified in Schedule 1 and Schedule 3 of the protocol. Descriptive statistics for change from baseline to post-baseline, and shifts with respect to normal ranges for the same period will also be presented. Data listings will be provided for all subjects. Laboratory values outside the normal range will be flagged.

Baseline is denoted as Visit 1.

Number of subjects with potentially clinically important (PCI) lab values will also be presented. Potentially clinically important lab values are defined as per Table 1 below.

\\SW20RND01\VistaTempDir\Temp28232\Shire\_0624\_209\_SAP\_v1 0.docx Document: Version Number: Author:

Reference: CS\_WI\_BS005

Version Date:

Template No: CS\_TP\_BS016 Revision 4

1.0

Table 1: Potentially important lab values

Test Item	Unit	Reference range	Criterion *1
WDC (11 B)	/micro L	2222 2222	> 15000
WBC (blood)		3300 - 9000	< 2000
Eosinophils (rel)	%	0.0 - 8.0	> 10.0
N	/micro L	(NT/A)	> 11000
Neutrophils (abs)		(N/A)	< 1000
Lymphocytes (abs)	/micro L	(N/A)	> 20000
Lymphocytes (abs)		(IV/A)	< 500
	g/dL	M: 13.5 - 17.5	>(BL) + 4.0
hemoglobin (blood)		F: 11.5 - 15.0	· (DL) · 4.0
		11110 1510	<(BL) – 3.0
platelet count	x10^4	14.0 - 34.0	> 60.0
	/micro L		< 10.0
aPTT-second	sec	25.0 - 36.0	> 90.0
PT-INR	(N/A)	0.85 - 1.15	> 2.875
BUN	mg/dL	8 - 23	> (BL) x 2.0
creatinine	mg/dL	M: 0.61 - 1.04 F: 0.47 - 0.79	> (BL) x 2.0
1 ( )	mg/dL	70 100	> 250
glucose (serum)		70 - 109	< 40
1.	mEq/L	127 147	> 155
sodium		137 - 147	< 130
	mEq/L	25.50	> 6.0
potassium		3.5 - 5.0	< 3.0
AST	U/L	10 - 40	> 200
ALT	U/L	5 – 45	> 225
ALP	U/L	100 - 325	> 1625
CPK	U/L	M: 60 - 270	M: > 1350
CPK		F: 40 - 150	F: > 750
total bilirubin	mg/dL	0.2 - 1.2	> 3.6
calcium	mg/dL	8.4 - 10.4	> 12.5
calcium		8.4 - 10.4	< 7.0
phosphorus	mg/dL	2.5 - 4.5	< 2.0

\*1 BL (Baseline) is Visit 1. When the sample is not collected at Visit 1, the alarm for variation (ratio/difference) is not performed.

\\SW20RND01\\VistaTempDir\Temp28232\\Shire\_0624\_209\_SAP\_v1 0.docx Version Number: Document: Author:

Version Date: 21Jul2017 Reference: CS\_WI\_BS005

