#### 5.8.4. VITAL SIGNS PARAMETERS

Vital sign will be measured at the time points specified in Schedule 1 and Schedule 3 of the protocol. Additional vital signs measurements may be performed during the study if clinically indicated. On dosing days, vital signs should be obtained ≤30 minutes before the start of the infusion, ≤15 minutes after completion of the infusion, and between 30 minutes and 1 hour after completion of the infusion.

Summary statistics for vital signs measured at each treatment visit, and the change from post-infusion to pre-infusion at each visit, will also be presented.

Number of subjects with PCI vital signs data will also be presented. Potentially clinically important vital signs values are defined as follow:

Variable	Potentially Clinically Important Criteria
Systolic Blood Pressure	< 90 mmHg;
	≥ 140 mmHg.
Diastolic Blood Pressure	< 60 mmHg;
	≥ 90 mmHg.
Pulse	≤ 50 bpm;
	≥ 100 bpm.

Height and weight, obtained at the screening visit, will be summarized within the demographics table.

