Table 14.3.1.3.2 Serious Treatment-emergent Adverse Events by Preferred Term (Intent-to-Treat Safety Analysis Set

Table 14.3.2.1 Treatment-emergent Adverse Events by Maximum Severity, System Organ Class and Preferred Term (Intent-to-Treat Safety Analysis Set)

Table 14.3.2.2 Treatment-emergent Adverse Events Considered Related to Investigational Product by System Organ Class and Preferred Term (Intent-to-Treat Safety Analysis Set)

Table 14.3.4.1 Quantitative Clinical Laboratory Results: Hematology (Intent-to-Treat Safety Analysis Set)

Table 14.3.4.2 Quantitative Clinical Laboratory Results: Clinical Chemistry (Intent-to-Treat Safety Analysis Set)

Table 14.3.4.3 Quantitative Clinical Laboratory Results: Coagulation (Intent-to-Treat Safety Analysis Set)

Table 14.3.4.4 Quantitative Clinical Laboratory Results: Urinalysis (Intent-to-Treat Safety Analysis Set)

Table 14.3.4.5 Shift from Baseline in Clinical Laboratory Results: Hematology (Intent-to-Treat Safety Analysis Set)

Table 14.3.4.6 Shift from Baseline in Clinical Laboratory Results: Clinical Chemistry (Intent-to-Treat Safety Analysis Set)

Table 14.3.4.7 Shift from Baseline in Clinical Laboratory Results: Coagulation (Intent-to-Treat Safety Analysis Set)

Table 14.3.4.8 Shift from Baseline in Clinical Laboratory Results: Urinalysis (Intent-to-Treat Safety Analysis Set)

Table 14.3.4.9 Subjects with Potentially Clinically Important (PCI) Laboratory Results (Intent-to-Treat Safety Analysis Set)

Table 14.3.5.1 Actual Values and Change from Baseline in Vital Signs (Intent-to-Treat Safety Analysis Set)

Table 14.3.5.2 Potentially Clinically Important Vital Signs Results (Intent-to-Treat Safety Analysis Set)

Table 14.3.6 Study Drug Exposure (Intent-to-Treat Safety Analysis Set)

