#### 9.1.3. LIST OF PLANNED LISTINGS

Listing 16.2.1.1 Subject Disposition (All Enrolled Subjects)

Document: \\SW20RND01\\VistaTempDir\Temp28232\\Shire\_0624\_209\_SAP\_v1 0.docx

Author: PPD Version Number: 1.0
Version Date: 21Jul2017

Template No: CS TP BS016 Revision 4 Reference: CS WI BS005

Shire
PROTOCOL: 0624-209
Page 31 of 35

Listing 16.2.1.2 Subjects Who Terminated from the Study (All Enrolled Subjects)

Listing 16.2.2.1 Deviations from Inclusion/Exclusion Criteria (All Enrolled Subjects)

Listing 16.2.2.2 Protocol Deviations (All Enrolled Subjects)

Listing 16.2.4.1 Subject Demographic and Baseline Characteristics (Intent-to-Treat Safety Analysis Set)

Listing 16.2.4.3.1 Hereditary Angioedema (HAE) History (Intent-to-Treat Safety Analysis Set)

Listing 16.2.4.3.2 Hereditary Angioedema (HAE) History Detail (Intent-to-Treat Safety Analysis Set)

Listing 16.2.4.3.3 Medical History (Intent-to-Treat Safety Analysis Set)

Listing 16.2.4.4.1 Prior and Concomitant Medications (Intent-to-Treat Safety Analysis Set)

Listing 16.2.4.4.2 Concomitant Medical/Surgical Procedures (Intent-to-Treat Safety Analysis Set)

Listing 16.2.5.2.1 Study Drug Administration (Intent-to-Treat Safety Analysis Set)

Listing 16.2.5.2.2 Study Drug Exposure (Intent-to-Treat Safety Analysis Set)

Listing 16.2.5.3 C1-INH Antigen, Functional C1-INH activity, Complement C4 and C1q (Intent-to-Treat Safety Analysis Set)

Listing 16.2.5.4 Antibody Results (Intent-to-Treat Safety Analysis Set)

Listing 16.2.6.1 Subject Data of Angioedema Attack (Intent-to-Treat Safety Analysis Set)

Listing 16.2.6.2 Subject Data of Breakthrough Attack (Intent-to-Treat Safety Analysis Set)

Listing 16.2.6.3 Investigator Assessment of Breakthrough Attack (Intent-to-Treat Safety Analysis Set)

Listing 16.2.6.4 Self-administration Survey (Intent-to-Treat Safety Analysis Set)

Listing 16.2.6.5 Treatment Compliance (Intent-to-Treat Safety Analysis Set)

Listing 16.2.7.1 Adverse Events (Intent-to-Treat Safety Analysis Set)

Listing 16.2.7.2 Serious Adverse Events (Intent-to-Treat Safety Analysis Set)

Listing 16.2.8.1.2 Clinical Laboratory Test Results (Intent-to-Treat Safety Analysis Set)

Listing 16.2.8.1.3 Subjects with Potentially Clinically Important Laboratory Test Results (Intent-to-Treat Safety Analysis Set)

Listing 16.2.8.2.1 Vital Signs (Intent-to-Treat Safety Analysis Set)

Listing 16.2.8.2.2 Subjects with Potentially Clinically Important Vital Signs (Intent-to-Treat Safety Analysis Set)

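### SAP 5.1 keeps unscheduled-visit values out of the PCI laboratory and vital-sign subject counts, so those counts can be too low and can disagree with the listings (minor)

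*SAP*

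**What the plan says.** SAP 5.1 sets a general rule: "Unscheduled visits data will not be included in analysis, otherwise specified". The clause does not parse as written, but the next sentence settles its meaning: "Unscheduled visits data will merely be presented in listings". The natural reading is exclusion unless otherwise specified.

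Two safety summaries then count subjects against fixed cut-offs:

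- SAP 5.8.2: "Number of subjects with potentially clinically important (PCI) lab values will also be presented". The cut-offs are in SAP Table 1.
- SAP 5.8.4: "Number of subjects with PCI vital signs data will also be presented". The cut-offs are in the table in that section.

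Neither sentence makes an exception for unscheduled values. SAP 9.1 plans Tables 14.3.4.9 and 14.3.5.2 for these counts, and Listings 16.2.8.1.3 and 16.2.8.2.2 for the subjects with PCI values. All four use the Intent-to-Treat Safety set.

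**The concern.** Restricting by-visit summaries to scheduled visits is sensible, because extra readings would distort the mean at a visit. A count of subjects who ever crossed a cut-off has a different purpose: it should show who had a markedly abnormal value, whenever it was taken.

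The protocol expects unscheduled values to arise where something may be wrong. Sections 6.3 and 6.7 allow extra vital signs and laboratory tests on clinical grounds. Section 9.1.5 asks for follow-up of new abnormal end-of-treatment values until they normalise or are explained. Leaving these values out removes readings that are more likely than routine ones to be abnormal. At stake is whether the PCI tables can be read as complete, and whether table and listing name the same subjects.

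**Working it through.** The documents state no figure on this point, so there is none to reproduce. The check is of the rule, its direction, the schedule and the size per subject.

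1. **Direction.** Let S be the subjects with at least one scheduled PCI value and U those with at least one unscheduled PCI value.
   - Count under SAP 5.1: |S|.
   - Count over all values: |S ∪ U| = |S| + |U not in S|.
   - The difference is |U not in S|, which is zero or positive. The planned count can therefore be equal or too low, never too high.

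2. **Laboratory schedule.** Protocol Schedule 1 places post-baseline hematology, chemistry and coagulation at Visits 8, 16 and 24, and note c puts the draws before infusion. In Schedule 3 these rows are marked only for the Early Discontinuation Visit.
   - A completer thus has 3 scheduled post-baseline safety draws, and 0 after the last dose.
   - With an average dose interval of 3.5 days, Visit k falls on about Day 1 + 3.5 × (k − 1). Visits 8, 16 and 24 fall on Days 25.5, 53.5 and 81.5, which is 28 days apart.
   - Assume an excursion of L days begins at a uniformly distributed time between Day 1 and Day 81.5, a span of 80.5 days. Three draws then catch a share of about 3L/80.5: 3.7% for 1 day, 11.2% for 3 days, 26.1% for 7 days and 52.2% for 14 days.
   - These shares show how sparse the draws are. They do not estimate how many subjects the table would miss, because an excursion must also be caught by an unscheduled test before it can be listed and not counted.

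3. **Vital-sign schedule.** Schedule 1 has vital signs at 13 dosing visits (1, 2, and every even visit from 4 to 24).
   - Subjects who independently self-administer at home skip Visits 10, 12, 14, 18, 20 and 22. If all six are done at home, 13 − 6 = 7 visits remain.
   - Protocol 6.3 asks for three readings per dosing visit, two of them after infusion. That gives 13 × 3 = 39 or 7 × 3 = 21 scheduled readings, including post-infusion readings at Visit 24.
   - An only PCI value that happens to be unscheduled is correspondingly less likely than for laboratory tests.

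4. **Example.** In SAP Table 1 the AST reference range is 10 to 40 U/L and PCI is above 200 U/L. A new Visit 24 value between 41 and 200 is abnormal but not PCI. Protocol 9.1.5 calls for follow-up. If a repeat a few days later exceeded 200, it would be listed but the subject would not be counted.

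5. **Size per missed subject.** The shift is 1/N. The number treated is not given; SAP 3.2 gives only a minimum of 6 completers.
   - Assumed N = 6: 1/6 = 16.7 percentage points.
   - Assumed N = 8: 12.5 points. Assumed N = 10: 10.0 points.
   - At N = 6 the table would show 0/6 (0%, exact 95% CI 0 to 45.9%) instead of 1/6 (16.7%, 0.4 to 64.1%).

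**The case against.** The best defence is that this is a declared convention. SAP 5.1 says both what is excluded and where it goes, so a scheduled-data table beside an all-data listing is the design described, not a contradiction. Nothing is hidden: SAP 5.8.2 provides laboratory listings for all subjects with out-of-range values flagged, and full Listings 16.2.8.1.2 and 16.2.8.2.1 are planned besides the PCI listings. A change the Investigator judges clinically significant is an AE under protocol 9.1.5. In a study this small a reader can go through the values by eye. Moreover, no sentence says that the PCI listings in particular include unscheduled values; that follows only from the general rule in 5.1.

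Most of this stands, and it is why the point is minor. Two things remain. The AE route depends on judgement, whereas PCI is a fixed cut-off, so a value can meet the cut-off without becoming an AE. And the convention, however openly stated, works in one direction on a safety count. The mention of additional vital signs in SAP 5.8.4 does not supply the exception: it repeats protocol 6.3 and says nothing about the count.

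A reader might also infer that the whole month after the last dose is a blind period for safety. The documents do not support that. The treatment-emergent window in protocol 7.4 ends 7 days after the last dose, so most of that month lies outside it. Scheduled PK/PD samples after the Visit 24 infusion and a 1-month antibody sample also exist. Only safety laboratory tests lack a scheduled draw after a completer's last dose.

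**Conclusion.** The point holds as a minor one. Under SAP 5.1, read with the missing unless supplied, the PCI counts in 5.8.2 and 5.8.4 leave out unscheduled values. They can only be equal to or below the count over all values, and a listed subject may not be counted. The laboratory table is the main concern; the vital-sign table is a lesser one.

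The size is one subject in N for each subject whose only PCI value is unscheduled, with N assumed. How many such subjects there are cannot be known from the documents, and the number may be zero. It would go too far to say that the counts are in fact wrong or that safety findings are suppressed: the documents contain no results, and the values stay in the listings.

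**What to change.** - **SAP 5.1:** correct the clause to read unless otherwise specified, and keep by-visit summaries on scheduled visits.
- **SAP 5.8.2 and 5.8.4:** state that the PCI subject counts use all scheduled and unscheduled values after the first dose through 7 days after the last dose, and that later values are listed only. Cite protocol 7.4 for the window, because the definition of treatment-emergent events in SAP 5.8.1 does not repeat the 7 days. Without an end date, open-ended follow-up under protocol 9.1.5 could bring late values into the count.
- **Tables 14.3.4.9 and 14.3.5.2:** show the scheduled-only count beside the all-values count.
- **Local-laboratory values:** count them too, converted to the Table 1 units and footnoted. Protocol 6.7 lets clinically indicated tests be run locally and has sites enter the results in the CRF. Leaving them out would recreate the mismatch between table and listing. The footnote matters most for hemoglobin, BUN and creatinine, whose cut-offs are relative to the Visit 1 value.

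The cost is a sentence or two in each of two sections, one corrected clause, one extra count in two tables and some unit conversion. The downside is that counts may rise, and subjects tested more often have more chances to cross a cut-off. Keeping the scheduled-only count alongside lets the reader see that effect.
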